2.5. Vitamin D in T1D

As noted above, the observation that cod liver oil was associated with lower risk of T1D suggests the possibility of a synergistic effect of both of the components of cod liver oil (DHA and vitamin D) (Stene and Joner, 2003). A large retrospective cohort study demonstrated an association between vitamin D supplementation in the first year of life and a lower risk of T1D [24]. This association was also demonstrated in a prospective study in which infants received vitamin D supplementation (Stene et al., 2000; Stene and Joner, 2003). The mechanism may be related to the immunosuppressive properties of Vitamin D or possibly a direct effect on islet cell insulin secretion. Vitamin D receptor (VDR) gene polymorphisms have recently been associated with susceptibility to T1D in humans (Alician et al., 2009; Lowe et al., 2007). Interestingly, Stene et al (2000) found an indication for a protective effect with certain polymorphisms, but this was strongest for children who took cod liver oil during the first year of life.

Serum 25-hydroxyvitamin D (25-OHD) concentrations are largely determined by environmental factors, mainly through vitamin D intake and ultraviolet exposure. The sun is the primary source of vitamin D, which is synthesized endogenously in skin to produce cholecalciferol (vitamin D3), although a small proportion (<20%) of vitamin D comes through diet from a limited range of foods (in the form of ergocalciferol [vitamin D2] and vitamin D3) (Holick 2006). The main marker of vitamin D status is the metabolite 25-OHD, which is synthesized in the liver (Chiu et al., 2004; Norman et al., 1980).

A relationship between type 1 diabetes mellitus and vitamin D deficiency has been reported (Luong et al., 2005; Mathieu et al., 2005). The prevalence of vitamin D deficiency in patients with type 1 diabetes was 15% to 90.6% (Greer and Rogers, 2007; Svoren et al., 2009; Bener et al., 2009). There is evidence that vitamin D is important in the prevention of islet cell death and might be useful in improving the survival of islet cell grafts, and it improves the production of insulin. Low vitamin D levels were shown to have a negative effect on beta-cell function (Chiu et al., 2004; Norman et al., 1980). Regular doses of vitamin D early in life have been shown to reduce the risk of developing type 1 diabetes (Luong et al., 2005). Vitamin D treatment has also been shown to improve glycemic control and insulin sensitivity in people with type 1 and type 2 diabetes and in normal individuals. Increasing vitamin D levels from 25 to 75 nmol/L results in a 60% improvement in insulin sensitivity. (Chiu et al., 2004; Norman et al., 1980). Borissova et al., 2003; Gedik and Akalin 1986; Schwalfenberg 2008). These effects have been mainly attributed to the immunomodulatory actions of vitamin D (Luong et al., 2005).

Geographic location seems to play a part in the development of type I diabetes with risk increasing as farther from the equator. The location on Earth contributes to the amount of vitamin D the body produces. This observation is suggestive, but not proof, that vitamin D affects the development of type 1 diabetes. Finland, a country that is at latitude far from the tropics, has the highest incidence of type 1 diabetes in the world. In the late 1960s, it was common to supplement an infant's diet with 2,000 IU

vitamin D. When researchers compared the development of type 1 diabetes in people 30 years later based on whether their mothers recalled giving them vitamin D during the first year after birth, they found an 80 percent reduction in the risk of type 1 diabetes later in life. Calcitriol makes insulin-secreting beta cells resistant to immune system attack. The active vitamin appears to reduce the production of cytokines, substances that kill beta cells.

Currently, project NCT03046927 conducted at the University of Massachusetts, Worcester is studying the role of vitamin D supplementation on the honeymoon phase of type 1 diabetes in children who are on standardized insulin treatment. The investigation is based on hypothesis that early intervention with vitamin D lead to significant changes in the approach to the early phase of type 1 diabetes with a strong emphasis on prolonging the honeymoon phase by using vitamin D and maintaining these patients on a standardized insulin regimen. The study rationale also indicates role of vitamin D in reducing the long-term complications of type 1 diabetes.

3. STUDY RATIONALE

The anti-inflammatory properties of omega-3 long-chain polyunsaturated fatty acids (LCPUFA) [eicosapentaenoic acid (EPA) and docosahexaenoic acid (DHA)] have been extensively reported in the literature. Derivatives from omega-3 LCPUFA have been associated with marked anti-inflammatory effects whereas arachidonic acid (AA), an omega-6 LCPUFA, is the precursor of eicosanoids associated with pro-inflammatory properties. Thus, a high AA/EPA ratio would suggest that the balance is shifted towards a pro-inflammatory state. Treatment with omega-3 fatty acids aimed at lowering the AA/EPA ratio may then prove to be beneficial particularly in diseases associated with a high inflammatory state. Bioactive metabolites such as resolvins and protectins are derived from omega-3 fatty acids and are postulated to mediate the anti-inflammatory properties of omega-3 fatty acids. These mediators act by several mechanisms including reduction of neutrophil infiltration, attenuation of TNF stimulated NF- κ B activation, inhibition of interleukin-1 β (IL-1 β), reduction in tumor necrosis factor (TNF) and interferon- γ secretion, inhibition of T-cell migration and regulation of T-cell apoptosis. Notably, IL-1 β and TNF have both been implicated in beta-cell death and IFN signatures as well as T cell infiltration of the pancreatic islets have been associated with type 1 diabetes (T1D).

A number of studies suggest that omega-3 fatty acids may be beneficial in T1D:

- Bellenger et al. reported that transgenic fat-1 mice, a model of endogenous omega-3 LCPUFA synthesis, were protected against streptozotocin-induced diabetes. This protection was associated with a reduction in pro-inflammatory cytokines with a concomitant increase in anti-inflammatory cytokines.
- The Diabetes Autoimmunity Study in the Young (DAISY) follows children at high risk for T1D development; in this study, dietary intake of omega-3 fatty acids was associated with a reduced risk of developing islet autoimmunity, especially of developing multiple autoantibodies, which are a strong risk factor for future disease. There was no association with the development of T1D.

- The Nutritional Intervention to Prevent (NIP) Type 1 Diabetes Study was a pilot study which evaluated the effect of DHA supplementation on inflammatory cytokine levels in infants at high genetic risk for T1D. Although DHA supplementation of infant diets was found to be safe, inflammatory cytokine production was not consistently reduced. However, the study was not designed to adjust dietary intake of omega-3 fatty acids to target specific AA/EPA ratios and it is unclear whether reaching specific ratios may translate into improved clinical outcomes.

However, in a pilot study of T1D patients with established disease (>4 years duration) omega-3 fatty acids failed to improve glycemic control after 4 weeks of therapy. This may suggest that anti-inflammatory therapies may need to be introduced early in the course of T1D in order to have an impact on prevention of beta-cell loss. In addition, considering that T1D is a chronic autoimmune and inflammatory disease, anti-inflammatory strategies may need to be administered over a prolonged period of time in order to observe a clinical benefit.

The anti-inflammatory properties of vitamin D are well established. In particular, it has been shown that Vitamin D prevents both insulitis and type 1 diabetes mellitus in mouse models of T1D and retrospective studies have shown apparent beneficial effects of vitamin D supplementation in early life on successive lifetime risk of T1DM. Vitamin D has been linked to several immunomodulatory effects. Studies in new onset T1D have shown that treatment with cholecalciferol (vitamin D3) results in both an increase in the percentage and the suppressive capacity of regulatory T-cells. A recent study in adults with vitamin D deficiency showed that daily treatment with 4,000 IU of vitamin D3 significantly reduced CD4+ T-cell activation compared to treatment with 400 units of vitamin D3. However, the role of vitamin D in preservation of beta-cell function in new onset T1D is controversial. Two studies showed no significant effect of therapy with calcitriol (1,25(OH)2D3) whereas one study using 2,000 IU of cholecalciferol daily showed a higher stimulated C-peptide at 18 months compared to placebo. Further studies evaluating the role of vitamin D supplementation in prevention of beta-cell loss at T1D onset are warranted.

Considering the safety profile and anti-inflammatory properties of high dose omega-3 fatty acids combined with Vitamin D supplementation makes this therapy a possible candidate for T1D intervention trials.

4. STUDY DESIGN

4.1. Overview

Based on the findings presented in this document, we propose to test the safety and efficacy of a regimen that combines Omega-3 Fatty Acids and Vitamin D in a design that considers timing and duration of administration in relation to their effects and predicted synergies. These agents may promote sustained immune regulation, reduce inflammation, and provide support for the residual beta cell mass. This integrated therapeutic regimen addresses major pathogenic mechanisms in T1D and thus represents a rational and well supported approach to preserve insulin secretion in T1D. This approach could halt the disease progress, preserve β -cell function and hopefully reduce dose of insulin required to manage T1D. Even partial beta cell function can facilitate disease management, reduce the likelihood of severe hypoglycemia and is associated with reduced risk of chronic complications. We hypothesize that Omega-3 Fatty Acids and Vitamin D, administered to patients with newly or

established T1D and residual stimulated C-peptide secretion will be safe and may preserve insulin secretion;

The safety will be measured by the AE profile. In addition, potential decreases in hypoglycemic events will be evaluated as this may be expected to be one of the clinical indications where combination therapy is likely to exert a clinical benefit. Other measures include the ability of combined supplement therapy to increase insulin production as assessed by serum C-peptide measurements, changes in exogenous insulin dose, and measurements of glycemic control.

The study endpoints vary between the two arms and include safety, tolerability, and efficacy. Safety endpoints include AEs over one year of treatment and an additional one year of follow-up (total two years). Efficacy endpoints include the ability of combining supplement products to produce insulin, assessed by serum C-peptide measurements following a Mixed Meal Tolerance Test (MMTT), changes in recorded exogenous insulin dose and other measures of glycemic control.

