4.2.2. Secondary Objective(s)

- Stimulated C-peptide area under the curve (AUC) during a 4-hour MMTT greater or equal to baseline level, at the 1 year visit.
- Reduction in HbA1c at the one year visit compared to baseline.
- Reduction in insulin requirement at the 1 year visit compared to baseline.
- Incidence of adverse events (AE) comparable to general diabetes population.

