4.3. Investigational Plan

This is a randomized, open-label, parallel-group, pilot phase I/IIa clinical study. Approximately 56 subjects will be randomly assigned to receive either Omega-3 Fatty Acids and Vitamin D combination or Vitamin D alone. All subjects will be given Vitamin D supplement. Patients to be included in this study are those diagnosed with new onset T1D (diagnosed within the last 180 days) or with established T1D (more than 6 months).

Participation for each subject will last approximately 2 years. Potential participants will have a screening visit to review their overall health, measure diabetes T1D-associated autoantibodies and perform a MMTT, which will also serve as the baseline MMTT. Eligible subjects will be invited to participate in the intervention trial for one year, and then followed for a second year to monitor safety and whether any potential therapeutic benefit, whether metabolic, endocrine, and/or immunological, persists after the therapy has been stopped.

We will evaluate beta cell function by examining C-peptide responses during a MMTT.

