4.9. Post-treatment Follow-up

All subjects will be treated with supplement combination or vitamin D alone over a one year period. Subjects will also be asked to undergo additional follow-up post-treatment for up to one year with a visit every 4 months.

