8.1. Data Collection, Monitoring, and Transfer

Adverse events will be collected from the initiation of study drug and be followed to resolution or until 30 days after the participant completes participation, whichever comes first.

Adverse events may be collected as follows:

- Observing the participant.
- Questioning the participant in an objective manner.
- Receiving an unsolicited complaint from the participant.

An abnormal value or result from a clinical or laboratory can also indicate an adverse event. If this is the case, then the evaluation that produced the value or result should be repeated until the value or result returns to normal or can be explained and the participant's safety is not at risk. If an abnormal value or result is determined by the investigator to be clinically significant, it must be indicated as such on the appropriate laboratory evaluation form(s), and must also be reported as an adverse event on the adverse event form. Abnormal vital sign measurements or laboratory finding deemed not clinically significant by the site investigator must be documented as such and are not required to be listed in the

adverse event source documents or adverse event case report form. The DRI will perform data collection, monitoring, and transfer tasks. A Clinical Research Monitor designated by Sponsor will be responsible for monitoring the clinical study in accordance with current federal and relevant foreign regulations. The Monitor will periodically collect the CRFs and brought them to Sponsor. Data on CRFs will be double-entered into the database system and verified.

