9.5.2. Interim Analysis of Safety Data

Interim analysis may be conducted as recommended by the DSMB, to review safety data, including metabolic, immunological assessments and adverse events. The DSMB may recommend early stopping if there is sufficient evidence to conclude that the investigational treatment is harmful based on interim analysis of safety endpoints.

At any time, if there are significantly more adverse events in the experimental arm based on Fisher's exact tests for comparison, early termination should be considered. For example, a scenario where 9 patients have enrolled with 6 in the combination treatment arm and 3 in the vitamin D alone arm with 5 adverse events in the combination treatment arm and 0 in the vitamin D treatment arm would be considered significantly increased likelihood of adverse events in the combination treatment arm and would potentially result in trial termination. The same holds in the scenario where 15 patients have been enrolled with 10 in the combination treatment arm and 5 in the vitamin D alone treatment arm, where the combination treatment group experiences 9 adverse events while the vitamin D group experiences only 1. Similar scenarios exist throughout the trial and at any time if the exact test comparing groups under the null that the likelihood of adverse events is equal between groups exceeds a significance threshold of 0.05, this would warrant early termination.

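### The adverse-event endpoint spans two years although study drug stops at one, and no on-treatment window is set, so harm confined to treatment is diluted

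*Combined protocol and SAP*

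**What the plan says.** Section 4.1 sets the safety window: "Safety endpoints include AEs over one year of treatment and an additional one year of follow-up (total two years". Section 4.9 limits treatment to the first year: "All subjects will be treated with supplement combination or vitamin D alone over a one year period". Section 4.3 describes the second year as a period for monitoring safety and whether any benefit "persists after the therapy has been stopped".

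Section 8.1 opens the collection period ("Adverse events will be collected from the initiation of study drug") and closes with "until 30 days after the participant completes participation, whichever comes first". That last clause may govern only how long an event is followed. On either reading, collection has no cut-off at the end of treatment, and Appendix A schedules AE assessment at every visit from month 4 to month 24.

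The AE objective in section 4.2.2, repeated in 9.2, is "Incidence of adverse events (AE) comparable to general diabetes population". It names no window and does not use Arm B as the reference. The only between-arm AE comparison is the monitoring rule in section 9.5.2, which uses Fisher's exact test at 0.05: "At any time, if there are significantly more adverse events in the experimental arm". It names no window either. Section 9.4 contains no AE analysis, and no section defines a treatment-emergent event or a separate year-1 table.

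**The concern.** About half of the AE observation time is off study drug in both arms. Section 7.1.1.1 counts Level 2 and Level 3 hypoglycemia as AEs, and section 7.1.6 requires a report form for every event of Grade 2 or above. Background events will therefore continue in both arms in year 2. The omega-3 effects listed in sections 5.4.1.3 and 5.4.8 are mainly gastrointestinal, and the plan gives no reason to expect them to outlast dosing.

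An excess that exists only while omega-3 is taken would shrink in a two-year figure. The trial could then report similar AE incidence in the two arms although the treatment year differed. The same mixing enters the 9.5.2 comparison as early participants pass month 12. Safety is in the title of this pilot, and half of the planned participants are children. The trial is also open label, so an unspecified window could be chosen after the data have been seen by arm.

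**Working it through.** **The plan's own figures.** The plan states no AE rate, safety power or detectable difference. What can be reproduced are the two Fisher examples in 9.5.2: 5/6 v 0/3 gives p = 0.048, and 9/10 v 1/5 gives p = 0.017. Both are significant at 0.05, as the section says.

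**Inputs.** From the documents: 28 per arm (4.6), Fisher's exact test at 0.05 (9.5.2, sidedness not stated, two-sided used here), one year on and one year off treatment (4.1, 4.9). Assumed: the year-1 risks of at least one AE, p0 (vitamin D alone) and p1 (combination).

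**Base case.** The excess ends with treatment, and in year 2 both arms have the control's year-1 risk. The two-year risks are:

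- control: 1 − (1 − p0)²
- combination: 1 − (1 − p1)(1 − p0)

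For 20% v 55% these are 1 − 0.8² = 36% and 1 − 0.45 × 0.8 = 64%. The 35-point difference becomes 28 points. Exact power for a single comparison:

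| Year-1 risks | Two-year risks | Difference (points) | Power, year 1 | Power, two years | Relative loss |
|---|---|---|---|---|---|
| 5% v 35% | 9.75% v 38.25% | 30 → 28.5 | 74% | 62% | 17% |
| 10% v 40% | 19% v 46% | 30 → 27 | 66% | 49% | 25% |
| 20% v 55% | 36% v 64% | 35 → 28 | 71% | 44% | 38% |
| 30% v 65% | 51% v 75.5% | 35 → 24.5 | 66% | 38% | 42% |
| 40% v 75% | 64% v 85% | 35 → 21 | 68% | 33% | 51% |
| 50% v 85% | 75% v 92.5% | 35 → 17.5 | 75% | 27% | 64% |

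If p1 is instead chosen to give 80% power on treatment, the relative loss is 8%, 15% and 21% at control risks of 2%, 5% and 10%. It is 33%, 35%, 47% and 62% at 20%, 30%, 40% and 50%.

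**Lower year-2 ascertainment.** With the year-2 hazard halved, 1 − p0 for year 2 becomes (1 − p0)^0.5. Two-year power is then 55% (20% v 55%), 49% (40% v 75%) and 48% (50% v 85%), against 44%, 33% and 27%.

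**Partial persistence.** If half of the excess hazard continues in year 2, the combination arm's two-year risk is 1 − (1 − p1)^1.5 × (1 − p0)^0.5. Power from year 1 to two years is then 66% to 77% for 10% v 40% (a gain), 58% to 58% for 20% v 50%, and 79% to 77% for 30% v 70%. At higher control risks some loss remains: 68% to 55% for 40% v 75%, and 75% to 44% for 50% v 85%.

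**Event counts.** A rate ratio RR confined to year 1 becomes (RR + 1)/2 over two years, so 2.0 becomes 1.5. The test statistic shrinks by √((RR + 1)/(RR + 3)), which for RR = 2 is √(3/5) = 0.775. Power of 80% falls to 58%, a 27% relative loss. The loss is 31% at RR 1.5 and 21% at RR 3.

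**The 9.5.2 rule with repeated looks.** This was simulated with six-monthly looks, uniform enrolment over three years, constant hazards, harm ending at month 12, and two-sided 0.05 at each look. The probability of crossing at some look, pooled window against on-treatment window, was 72% v 81% (20% v 55%), 69% v 78% (40% v 75%) and 73% v 85% (50% v 85%). The losses are 9, 9 and 12 points.

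**The case against.** The strongest reply is that the plan contains no final two-year between-arm AE test. Section 4.1 says that safety endpoints include these events, which describes how long AEs are observed and does not forbid a year-1 table. The AE objective refers to the general diabetes population. The Fisher test is a monitoring rule, and its early looks use on-treatment data only: the 90-day review of the first 24 participants (6.11) and DSMB reviews every three to six months (7.1.6). All of this stands, and it means the single-look powers do not describe how the monitoring rule will behave. It narrows the problem without removing it: under repeated looks the pooled window still gives up 9 to 12 points, and no section supplies the missing window.

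A reader might infer that pooling costs a third or more of the trial's power to see omega-3 harm. The documents do not support that. They state no safety power and no AE rates. The loss is 17% to 25% for control risks of 5% to 10% in the table, and it vanishes or reverses at control risks of 10% to 30% if half of the excess persists.

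A reader might also infer that laboratory AEs can hardly appear in year 2, because CBC and chemistries stop at month 12 in Appendix A. But PT/INR, HbA1c, vitamin D and AA/EPA testing continue to month 24, and PT is the test that section 5.4.1.3 names for clotting. Lower ascertainment in year 2 would also reduce the dilution.

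Year 2 has a stated safety purpose (4.3), so the follow-up itself should stay.

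**Conclusion.** The point holds in a limited form. The stated window is two years, the second year is off drug, and nothing separates the periods. Followed as written, the endpoint dilutes any AE excess that ends with treatment.

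The direction is certain for such an excess. The size is conditional on AE rates that the plan does not give. For a single two-sided Fisher comparison with 28 per arm, no carry-over and an unchanged background risk, power falls by 12 points at 5% v 35% (74% to 62%) and by 48 points at 50% v 85% (75% to 27%). A relative loss of a third or more needs events that affect about 20% or more of controls per year. That is plausible for any AE, since Level 2 hypoglycemia counts, but it is an assumption. It would not apply to uncommon events. This should be corrected because the remedy is cheap and fixes the window before the data are seen.

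**What to change.** Keep the two-year follow-up and all AE collection. Then:

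- In 4.1 and 9.2, make the main safety comparison the between-arm difference in AE incidence from first dose to the end of treatment, taken as the month-12 visit.
- Report AEs after the month-12 visit by arm as a separate period, with the two-year total as description only.
- In 9.5.2, state that the between-arm Fisher comparison uses the on-treatment window, while the DSMB continues to see all events from both periods.

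The cost is wording in three sections and one period flag derived from AE onset dates. No visits or samples are added. The small downside is that late effects are read from the separate year-2 table and not from a single total.
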